Randomised Controlled Trial Evaluation of "Putting Kitbag to Work"

Intervention Developer	International Futures Forum (IFF)
Delivery Organisations	International Futures Forum, University of Sussex
Evaluator	What Works for Children's Social Care
Principal Investigator	[name]
Protocol Author(s)	[name], [name], [name]
Type of Trial	Cluster Randomised Controlled Trial (2-arm; parallel design; multi-site)
Age or Status of Participants	Children and young people (aged 4-18 years old) on child in need plans, on child protection plans, or in care
Number of Participating Local Authorities	4
Number of Children and Families	c.9300 children aged 4-18 years old
Primary Outcome(s)	Children and young people: emotional literacy (as measured by the prosocial subscale of the Strengths and Difficulties Questionnaire)
Secondary Outcome(s)	
Children and young people:
 
 level of social care involvement (please see Outcomes section for operationalisation of measurement) behaviour (as measured by the total difficulties score of the Strengths and Difficulties Questionnaire) 
Social worker outcomes:
 
 self-efficacy (as measured by the competency subscale of the Work-Related Basic Needs Satisfaction scale) stress (as measured by the 8-item "Stress in General" scale) number of sick days 
Foster carer outcomes:
 
 self-efficacy (as measured by an adapted parental self-efficacy subscale of the "Me as a parent" scale)
Contextual Factors	Caseload (quantity and complexity)

Version

Version 1.1

This protocol has been updated to reflect the dropping of the primary data collection from the impact evaluation. The primary data collection has been dropped due to low numbers of consents to contact the child / young person collected.

The implication of dropping the primary data collection is restricting the outcomes to those that can be collected via administrative data or online surveys.

Table of contents

Randomised Controlled Trial Evaluation of “Putting Kitbag to Work”	1
Table of contents	2
Background and Problem Statement	4
Intervention and Theory of Change	5
Logic model	9
Impact Evaluation	10
Research questions	10
Design	10
Participants	11
Teams	12
Social workers and family support workers	12
Foster carers and kinship carers	13
Children and young people	13
Recruitment	14
Randomisation	14
Data collection	15

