If the sample is imbalanced with respect to team type (CIN / CP, CLA, children with disabilities) within the local authority, we will re-randomise (setting a new seed). We take imbalance to be the proportion of teams of that type within the local authority assigned to the intervention to be greater than 0.75 or less than 0.25 (i.e. $\frac{3}{4}$ or $\frac{1}{4}$ teams) except where there is only one team of that type in the local authority.

We will also report the mean proportion of social workers to family support workers, and the mean proportion of permanent staff to agency staff, by treatment allocation but will not re-randomise if there is imbalance in treatment allocation on these variables. With a relatively small number of teams to allocate, we have decided to prioritise team type (within the local authority) to enable us to compare the impact of the programme on these subgroups.

Data collection

We have several data collection methods:

Impact evaluation

- Children and young people:
 - administrative data to measure children's social care involvement
- Social workers:
 - online survey to measure self-efficacy, stress
 - administrative data to measure sickness absence
- Foster/kinship carers:
 - online survey to measure self-efficacy

⁷ Due to a delay of the required data from Oxfordshire County Council, the randomisation was conducted for the three other local authorities first, and the teams from Oxfordshire County Council were allocated separately.

Sample size / MDES calculations

		MDES (Proportion of a Standard Deviation)
MDES		0.127
Proportion of variance in child's outcome explained by:	Child covariates (including baseline measure)	0.8
	Social Worker team covariates	0.1 (3 covariates)
Intraclass correlations (ICCs)	Team	0.03
Alpha		0.05
Power		0.8
One-sided or two-sided?		Two-sided
Level of intervention clustering		Social worker team
Average cluster size		150 children in each team
Sample Size (children)	Intervention	4500
	Control	4500
	Total	9000
Sample Size (teams)	Intervention	30 (15 per local authority)
	Control	30 (15 per local authority)
	Total	60

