¹² Lundh, L.G., Wangby-Lundh, M., & Bjarehed, J. (2008). Self reported emotional and behavioral problems in Swedish 14 to 15-year-old adolescents: A study with the self-report version of the Strengths and Difficulties Questionnaire. *Scandinavian Journal of Psychology*, 49, 523–532.

¹³ <https://youthinmind.com/products-and-services/sdq/>

¹⁴ Scoring the Strengths & Difficulties Questionnaire for age 4-17. (2014).

<https://www.ehcap.co.uk/content/sites/ehcap/uploads/NewsDocuments/236/SDQEnglishUK4-17scoring-1.PDF#page=4>

¹⁵ Goodman A, Lamping DL, Ploubidis GB. When to use broader internalising and externalising subscales instead of the hypothesised five subscales on the Strengths and Difficulties Questionnaire (SDQ): data from British parents, teachers and children. *J Abnorm Child Psychol*. 2010 Nov;38(8):1179-91. doi: 10.1007/s10802-010-9434-x. PMID: 20623175.

¹⁶ Van den Broeck, A., Vansteenkiste, M., De Witte, H., Soenens, B., & Lens, W. (2010). Capturing autonomy, competence, and relatedness at work: Construction and initial validation of the Work-related Basic Need Satisfaction scale. *Journal of Occupational and Organizational Psychology*, 83(4), 981-1002.

¹⁷ Stanton, J. M., Balzer, W. K., Smith, P. C., Parra, L. F., & Ironson, G. (2001). A General Measure of Work Stress: The Stress in General Scale. *Educational and Psychological Measurement*, 61(5), 866–888. <https://doi.org/10.1177/00131640121971455>

more stress. The sixth secondary outcome measure is the mean of the responses for the 8 items¹⁸ where “no” is coded as 0, “?” is coded as 1.5 and “yes” is coded as 3 (2vi)¹⁹.

2iv) Days attended

The hypothesised lower stress may lead to fewer sick days of social workers. We measure this over the entire intervention period from T1 to T13. Instead of measuring the number of sick-days, we will instead measure the number of ‘days attended’ in work. This allows us to include social workers who leave their posts over the course of the trial - these individuals will be classified as absent every day after they leave. Excluding these participants from the absence analysis would risk biasing the results, as individuals’ likelihood to leave is correlated with their rate of sickness absence. The number of days not attended may include holidays and parental leave in addition to sickness absence. If possible, we will control for the number of days of holiday and parental leave.

Foster and kinship Carer Outcomes

2v) Self-efficacy

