Missing post-intervention data is a risk for this trial as some of the secondary outcomes are collected via primary data collection (an online survey) and the attrition is likely to be high given that the follow-up period is over a relatively long period of time (4 months - 12 months later) and the professionals may have left their employer.

Covariates

- If the covariate has more than 30% of the data missing, we will drop the covariate.
- For each covariate in the main model (see the “Covariates” section) that has up to 30% of the data missing, we will regress an indicator of missingness on the other covariates in the main model and outcomes using logistic regression, clustering the standard errors at the team level. If any of the coefficients on the covariates of the missingness model are statistically significant at the 5% level, then data is not missing completely at random (MCAR).
- To distinguish between whether the data is missing at random (MAR) i.e. missing conditional on observables or missing not at random (MNAR) i.e. missing conditional on unobserved variables, for all the covariates that were not MCAR we then impute the missing values of the covariate of interest (using a missing category for categorical variables and multiple imputation for numeric variables) and compare the treatment estimates using the imputed data and data restricted to the complete cases. If the results are similar (i.e. significant / insignificant, the same direction and only differing in magnitude of up to 20%), then data is likely to be missing at random (MAR). If the results are dissimilar, the data is likely to be missing not at random (MNAR).

If the data on covariates are MCAR or MAR, then complete case analysis is likely to be unbiased but less well powered. To maintain power we use a missing category for categorical variables as missingness is likely to be a predictor in itself and multiply impute missing numerical covariates (including pre outcome measures). We ignore the clustered structure of the data because cluster sizes are small, cluster follow-up rates may be highly variable and we expect the ICC to be low (we assume the ICC to be 0.03 in power calculations)²¹.

Outcomes

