- A table of baseline characteristics broken down by treatment arm and response to “pre” data collection and response to “post” data collection (including both those who remained in the sample and those who joined) to check whether characteristics have become more imbalanced by “post” data collection.
- Missing data is likely to be most problematic for data collected via primary data collection (vs routinely collected data). For the outcomes collected via routinely collected data, we will add in an indicator of missingness in the primary data collection and an interaction term between treatment and missingness in the primary data collection. The interaction term can be interpreted as the additional treatment effect on those who are missing from the primary data collection. This gives some proxy as to the likely direction and magnitude of attrition bias for the outcomes collected in the primary data collection.

Reporting

Some of the statistics we will report have been mentioned in earlier sections but we gather them here for ease of reference:

- For each outcome and covariate, we will report the percentage of missing data alongside summary statistics
- Rates of loss to “post” data collection for the arms of the trial
- A table of baseline characteristics broken down by treatment arm and response to “pre” data collection and response to “post” data collection (including both those who remained in the sample and those who joined)
- Description of sites (to allow for qualitative assessment of generalisability of findings)
- ICC at the team level (pre and post for all outcomes)
- Direction and standard errors of the site-treatment effects

Implementation and process evaluation

Aims

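### The treatment-by-missingness interaction is only one component of attrition bias, is not sufficient when response differs by arm, and has no child-level meaning in version 1.1

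*Protocol*

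**What the plan says.** Under Missing data strategy, Reporting, the protocol states that for outcomes from routine data "we will add in an indicator of missingness in the primary data collection", together with its interaction with treatment. It then explains: "The interaction term can be interpreted as the additional treatment effect on those who are missing from the primary data collection". The use to be made of that coefficient follows: "This gives some proxy as to the likely direction and magnitude of attrition bias for the outcomes collected in the primary data collection".

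Three other places bear on this.

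- Section 2iv) Days attended, the only routine outcome for staff, says of those who leave their posts that "these individuals will be classified as absent every day after they leave".
- The version note says "This protocol has been updated to reflect the dropping of the primary data collection from the impact evaluation", and adds: "The implication of dropping the primary data collection is restricting the outcomes to those that can be collected via administrative data or online surveys".
- The Data collection section lists a single source for children in the impact evaluation: "administrative data to measure children's social care involvement". The online surveys go to social workers, family support workers and carers.

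The IPE data collection schedule assumes a 10% survey response. The treatment-variable section expects about 80% of staff and carers in post at T0 still to be there at T13.

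**The concern.** Attrition bias in an arm comparison is the gap between the effect among respondents and the effect in everyone randomised. The planned coefficient answers another question: whether the arm difference is the same in non-respondents as in respondents. The two agree, up to a factor, only when the same share is missing in each arm. The protocol itself allows for large differential attrition, in Missing data strategy, Outcomes. Unequal response is also plausible because intervention staff receive the resource, have leads in their teams and are asked additional survey questions.

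A reader who takes the coefficient at face value could conclude that stress and self-efficacy results are little affected by non-response when respondents are in fact selected. The opposite error is possible for days attended, where leaving drives both the outcome and survey non-response.

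**Working it through.** **1. What the interaction measures.** The protocol gives no figure to reproduce, so the check is algebraic. Ignoring covariates, write the routine outcome as b0 + b1*D + b2*M + b3*D*M, with D treatment and M = 1 if the survey is missing. Let p1 and p0 be the missing shares in the intervention and control arms.

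- Intervention mean: b0 + b1 + (b2 + b3)*p1
- Control mean: b0 + b2*p0
- Full-sample effect: b1 + b2(p1-p0) + b3*p1
- Respondent-only effect: b1
- Bias = respondent-only minus full-sample = -[b2(p1-p0) + b3*p1]

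If p1 = p0 = p, bias = -p*b3: the interaction is then sufficient, with reversed sign. Otherwise the b2(p1-p0) term is missing from it.

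**2. Response that differs by arm and depends on the outcome.** Assumptions, not in the protocol: no treatment effect, a standard normal outcome, response when a normal latent variable passes a threshold, and correlation 0.5 between the two. With response rate r and φ the normal density at the threshold, the mean is 0.5φ/r in respondents and -0.5φ/(1-r) in non-respondents. Rates are intervention v control.

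| Response | Respondent contrast | Non-respondent contrast | b3 | Bias (SD) |
|---|---|---|---|---|
| 60% v 40% | 0.322 - 0.483 = -0.161 | -0.483 + 0.322 = -0.161 | 0 | -0.161 |
| 50% v 35% | 0.399 - 0.529 = -0.130 | -0.399 + 0.285 = -0.114 | +0.016 | -0.130 |
| 15% v 10% | 0.777 - 0.878 = -0.100 | -0.137 + 0.098 = -0.040 | +0.061 | -0.100 |

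The last row through the identity: b2 = -0.098 - 0.878 = -0.975 (from unrounded means), so bias = -[(-0.975)(0.85 - 0.90) + 0.061 × 0.85] = -[0.049 + 0.052] = -0.10. The interaction supplies -0.05 of it.

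In this model b3 = 0.5{φ0/[r0(1-r0)] - φ1/[r1(1-r1)]}. With unequal rates it is exactly zero only when the two rates sum to 100%.

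**3. Days attended and leavers.** From the protocol: about 20% leave, and they are coded absent afterwards. Assumed: leavers do not answer at T13 and average 110 days (uniform on 0 to 220), stayers average 210, stayers respond at random at 75% v 50%, and treatment has no effect.

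- Intervention non-respondents: 20% leavers and 80% × 25% = 20% stayers, so half are leavers; mean (110 + 210)/2 = 160.
- Control non-respondents: 20% leavers and 80% × 50% = 40% stayers, so one third are leavers; mean (110 + 2 × 210)/3 = 176.7.
- Respondents: 210 in both arms. All staff: 0.2 × 110 + 0.8 × 210 = 190 in both arms.

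So b3 = 160 - 176.7 = -16.7 days, while the effect and the bias are both zero. With stayers responding at 50% v 35%, the same steps give 176.7 - 182.2 = -5.6 days.

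**4. Child outcomes.** With no child survey, a child-level M equals 1 for every child. M then duplicates the intercept and D*M duplicates D, so b3 is not identified. Carers have a survey outcome but no routine one. The check can therefore be run only for staff, through days attended.

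**5. Power.** In simulations of 600 to 1,000 staff in 60 teams at 15% v 10% response, the interaction test rejected in 6-7% of trials and the direct respondent-minus-all comparison in 9-11%. Neither is sensitive at that response rate.

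**The case against.** The protocol claims only some proxy, attaches no threshold or decision to it, and lists it among summary statistics meant for qualitative assessment. That stands, and it is why the point is minor.

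Response by arm is also examined elsewhere. Missingness is always regressed on treatment, and loss rates and baseline characteristics by arm and response are always reported. In simulation (60 teams of 10-17 staff, ICC 0.03), a team-level test flags 60% v 40% in at least 99% of trials, which would lead to imputation within arm and the further sensitivity analyses. So a reader might infer that bias would pass unnoticed behind a null interaction. The documents do not support that for large response gaps. At 15% v 10%, however, the same test succeeds in only 37-51% of trials.

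A reader might also infer that the interaction is uninformative or has the wrong sign. It does not: it is defined as non-respondents minus respondents, so a positive value beside a negative bias is consistent. Exact cancellation needs particular response rates far from the assumed 10%.

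For children, a model using the worker's or carer's survey response could be fitted. None is specified, and it would describe staff or carer non-response.

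Finally, the direct comparison is itself imperfect. If treatment cut leaving from 25% to 15% and stayers responded at random, a survey outcome unrelated to leaving would have no bias, yet respondents minus all staff would show -10 days (0.20 SD) on days attended. That objection stands and limits what the replacement can claim.

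**Conclusion.** The concern holds as a minor correction. The interaction is one component of attrition bias, with reversed sign, and is sufficient for the routine outcome only when response is equal in both arms. Near the plan's assumed response it points the right way but implies about half the bias (-0.05 against -0.10 SD at 15% v 10%). At higher, unequal response rates it can be near zero with a bias of 0.13 to 0.16 SD. For days attended it can be about -17 days with no effect and no bias. These sizes rest on an assumed outcome-response correlation of 0.5, assumed arm-specific response rates and assumed day counts. The identity itself does not. That a child-level indicator is constant follows from version 1.1 alone.

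A reader might infer that the trial's effect estimates are compromised. They are not: the check feeds no estimate or decision rule, and the primary outcome comes from administrative data.

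**What to change.** For days attended, replace the interaction with two estimates from the same model, one in all eligible staff and one in survey respondents only. Report respondent-only minus all-staff with a team-level bootstrap confidence interval, beside response rates by arm.

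State that this measures bias for days attended only; that it is an imperfect proxy for stress and self-efficacy and can mislead if treatment affects leaving; and that it has little power at about 10% response. Delete the check for child outcomes.

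The cost is a wording change and one extra regression with its bootstrap. Absence records must be linked to survey response, which the present plan already requires.
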